Clinical outcomes: the incidence of death (cardiac and non-cardiac), hospitalizations (for HF, for other cardiac causes not related to HF, for non-cardiac reasons), medications use (number of HF medications, doses) will be recorded at each visit in every patient. Adjudication of events for research purposes will be performed by an *ad hoc* committee blinded to treatment allocation, based on all the data available in the chart including notes, pre-formatted sheets, laboratory and imaging modalities.

6) ENROLLMENT IN THE STUDY

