9.2 Definition of the events

The events adjudicated will include:

- Death;
- Cardiac death (in which a direct cause attributable to cardiac disease is present);
- Sudden cardiac death (in which cardiac death occurred out of the hospital and suddenly; or in the hospital due to ventricular arrhythmias unrelated to other concomitant cardiac conditions);
- Non-cardiac death (in which the event of death is considered not to be a direct consequence of cardiac disease);
- Hospitalization for any cause;
- Hospitalization for heart failure (in which the primary diagnosis for hospitalization is decompensated heart failure established as the finding at admission of all 2 conditions listed: *a.* dyspnea or respiratory distress or tachypnea at rest or with minimal exertion; *b.* evidence of elevated cardiac filling pressure or pulmonary congestion (at least one of the conditions must be met: pulmonary congestion/edema at physical exam OR chest X-ray; plasma BNP levels ≥ 200 pg/ml; or invasive measurement of left ventricular end-diastolic pressure > 18 mmHg or of pulmonary artery occluding pressure (wedge) > 16 mmHg);
- Outpatient worsening of heart failure (defined as the need for intravenous diuretic treatment or need for increase in oral diuretic dose, or new prescription for first or add-on diuretic);
- Acute myocardial infarction, as defined by the WHO consensus statement 4th edition;
- Unstable angina, or need for coronary revascularization;

- Cardiac tachy-or brady-arrhythmias leading to a new hospitalization or to prolongation of hospital stay;
- Acute renal failure (defined as an increase in plasma creatinine levels of 50% or 0.5 mg/L);
- Acute respiratory failure (not due to heart failure);
- Sepsis or other serious infection requiring antibiotic therapy;
- Acute stroke.

The analysis will consider time to first event and time to each event. It will also consider event rates at 1, 3 and 6 months, in order to favor comparisons with other studies. The number of days free of hospitalization during the first 1, 3 and 6 months will also be measured and compared between groups.

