10.2 Handling of Withdrawals

Patients who permanently stop study injection (whether due to adverse event, investigator decision, or patient decision) will be considered withdrawn from treatment. Patients that have withdrawn from treatment will still be offered to complete all the functional assessments to analyze data in an intention-to-treat strategy. Patients who have withdrawn from treatment will also be followed for the complete duration of 6 months follow-up to monitor for safety. Loss to follow-up can occur due to patients' withdrawal or unreported death. If patients are lost to follow up and their clinical condition cannot be established (alive vs dead, hospitalized vs not), they will be excluded from the initial analysis, and then reintroduced for sensitivity analysis considering all potential outcomes.

Patients will be considered withdrawn from study if they express a desire to stop active participation. However, the investigators will continue to record adverse events, hospitalizations, and survival in these patients from the electronic medical record in an observational manner unless these patients withdraw consent. Upon withdrawal of consent, no further information will be collected from those patients.

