11.1 Study Hypothesis

We hypothesize that IL-1 blockade with Anakinra will improve aerobic exercise performance and reduce hospital admission rates in patients with recently decompensated systolic HF. As the first step in testing this hypothesis, we propose a randomized, double-blinded, pilot study to determine the effect of anakinra on aerobic exercise performance over the course of 6 months. Although this pilot study will not be powered to detect differences in the 6-month hospital admission rates, we believe this study will provide an estimate of the potential effect. An improvement in aerobic exercise performance alone would represent a valuable achievement in this HF population, and would provide the rationale—especially if paired with a signal showing reduced readmission rates—for a subsequent Phase III clinical study to evaluate IL-1 blockade on the key outcomes of HF morbidity and mortality.

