11.3 Statistical Analysis

11.3.1 Demographics and Baseline Characteristics

Descriptive summaries of continuous measurements will be reported as median and interquartile ranges due to potential deviation from Gaussian distribution. Descriptive summaries of categorical measurements consist of frequencies, proportions and 95% confidence intervals, when applicable. All analyses will be conducted after database locking once all data has been gathered and electronically captured. All analyses will be based on the intention-to-treat principle (i.e., analyzing groups as randomized and including all patients with outcome data available). The difference in interval changes in peak VO_2 at 24 weeks between the anakinra vs. placebo groups will be compared using random-effect analysis of variance for repeated measures to analyze the effects of treatment within each group and the effect of time_x_group allocation. Unadjusted p-values will be reported throughout, with statistical significance for the primary endpoint set at the 2-tailed 0.050 level. To evaluate the group differences in the secondary endpoints, data will be compared across all groups using the random-effect analysis of variance for repeated measures as indicated above for paired analyses, or Kaplan-Meier curves with Log-rank testing for event rates.

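### Section 9.2 compares hospitalization-free days over fixed windows without saying how death is scored; a literal count credits the days after death

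*Combined protocol and SAP*

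**What the plan says.** After listing the adjudicated events, Section 9.2 sets out how they will be analysed. It says "The analysis will consider time to first event and time to each event", adds event rates at 1, 3 and 6 months, and ends: "The number of days free of hospitalization during the first 1, 3 and 6 months will also be measured and compared between groups". Death is a separate item on the same list, and one type is by definition partly an out-of-hospital event: "Sudden cardiac death (in which cardiac death occurred out of the hospital and suddenly".

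Section 5.2 also keeps the two outcomes apart, recording "the incidence of death (cardiac and non-cardiac), hospitalizations (for HF, for other cardiac causes not related to HF, for non-cardiac reasons". Section 11.3.1 offers "Kaplan-Meier curves with Log-rank testing for event rates" for events and a repeated-measures analysis for other secondary data; it names nothing specific to a count of days. The nearest rule on vital status is in Section 10.2. It concerns patients lost to follow-up whose condition cannot be established: "they will be excluded from the initial analysis, and then reintroduced for sensitivity analysis considering all potential outcomes". It does not cover patients known to have died.

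**The concern.** A day count over a fixed window needs a rule for patients who do not live through the window. Without one, death can look like a good result: the patient can no longer be admitted, so the remaining days are all free of hospitalization. The population has just been discharged after decompensated heart failure, and Section 9.2 itself foresees sudden death outside hospital, so the case is not remote.

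At stake is the direction of one between-group comparison. With unequal mortality, the arm with more deaths is favoured, and a survival benefit would not appear in the measure at all. The protocol recognises the general problem elsewhere: Section 11.3.2 cites survivorship bias as the reason for imputing peak VO2. The day count has no corresponding rule.

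**Working it through.** The plan states no figure for this measure, so there is none to reproduce. The power figures in Section 11.2 concern peak VO2 and do not bear on it.

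**Inputs from the documents.** Allocation 68 to anakinra and 34 to placebo (Sections 5.1 and 11.2). Pilot readmission at 6 months: 5% with 12 weeks of anakinra, 30% with placebo (Section 4).

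**Assumptions, because the documents are silent.** Windows of 30, 90 and 182 days; mean death at day 90; one stay of 5 to 7 days per readmitted patient.

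**Step 1: single patients.** Literal score = window − hospital days. Days alive and out of hospital = window − hospital days − days after death.

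| Patient | Literal score (30 / 90 / 182) | Days alive and out of hospital |
|---|---|---|
| Survivor, no admission | 30 / 90 / 182 | 30 / 90 / 182 |
| Survivor, one 7-day admission | 23 / 83 / 175 | 23 / 83 / 175 |
| Death at home on day 20, no admission | 30 / 90 / 182 | 20 / 20 / 20 |

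(The last entry is 19 if the day of death is not counted.) The literal score ties the death with the event-free survivor and ranks it 182 − 175 = 7 days above the survivor with one admission.

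**Step 2: arm means.** In each arm, the literal mean exceeds the mean of days alive and out of hospital by mortality × (182 − mean day of death). At mean day 90 the multiplier is 92 days. Mortality of 2%, 5% or 10% gives 0.02 × 92 = 1.8, 0.05 × 92 = 4.6 or 0.10 × 92 = 9.2 days. These are single-arm amounts. If mortality and its timing are equal in both arms, they cancel in the difference.

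**Step 3: the comparison.** What remains is (mortality in one arm − mortality in the other) × 92, that is 0.01 × 92 = 0.92 days per percentage point, in favour of the arm with more deaths. The assumed timing matters: mean death at day 30 gives 0.01 × 152 = 1.52 days per point, and at day 150 it gives 0.01 × 32 = 0.32.

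**Step 4: yardstick.** The pilot contrast is worth (0.30 − 0.05) × 5 = 1.25 to (0.30 − 0.05) × 7 = 1.75 days per patient. Repeat admissions would raise it. A mortality difference of 1.25 / 0.92 = 1.4 to 1.75 / 0.92 = 1.9 points opens a gap of that size between the two scorings. For example, with that excess of deaths on anakinra, the literal count would still show the full 1.25 to 1.75 days in its favour, while days alive and out of hospital would show no difference.

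**Step 5: one death.** One extra death on anakinra is 1/68 = 1.5 points, or 92/68 = 1.35 days. One extra death on placebo is 1/34 = 2.9 points, or 92/34 = 2.7 days.

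**The case against.** The strongest reply is that the plan is silent, not wrong. A reader might infer that Section 9.2 gives dead patients full credit, but it contains no scoring formula. An analyst could equally stop counting at death, which gives the day-20 patient about 20 days, or leave the patient out. That is fair, and the point is therefore that scoring is unspecified. It does not remove the problem: one patient can score 182, score about 20 or be excluded, and the literal reading is the one that goes wrong.

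Second, the measure carries little weight. Clinical outcomes are exploratory, Section 11.1 says "this pilot study will not be powered to detect differences in the 6-month hospital admission rates", and this count appears only in a closing sentence of Section 9.2. Deaths are adjudicated and analysed separately, so an imbalance would be seen beside it. This stands and limits the severity, although separate reporting does not change how the count itself is scored.

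Third, the size rests on assumed mortality, timing and length of stay. This also stands. The direction follows from the definition; the number of days does not.

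**Conclusion.** The concern holds as a minor point. Section 9.2 leaves the handling of death open, and the literal reading can rank an early death above a short readmission. Under the stated assumptions, the effect on the between-arm comparison is about 0.9 days per percentage point of mortality difference, and none if mortality and its timing are equal.

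Two stronger readings should be resisted. A reader might infer that this threatens the readmission signal wanted for Phase III. Section 11.1 describes that signal as "especially if paired with a signal showing reduced readmission rates", and rates are not altered by how this count is scored. Nor would a mortality difference erase the hospital days saved from the literal count; the count leaves out the days lost to death. A reader might also take the 1.8, 4.6 and 9.2 days as bias between arms. They are inflation of one arm's mean, and only the difference between arms matters.

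**What to change.** In Section 9.2, replace the measure with days alive and out of hospital in the first 1, 3 and 6 months. State that days after death count as zero. Report hospital days and days lost to death by arm as components.

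Add a rule for windows left incomplete by withdrawal of consent or loss to follow-up, since a full window cannot be observed for these patients. One option consistent with Section 10.2 is to exclude them from the initial analysis and bring them back in the sensitivity analysis over the possible outcomes. Known deaths are complete and stay in the initial analysis.

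The text should be fixed before unblinding. Section 9.3 places adjudication after study completion, and Section 7.2 releases the randomization log only after adjudication and database lock, apart from emergencies and monitoring-board requests.

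The cost is a few sentences. Deaths and hospitalizations are already recorded and adjudicated, so no visit or procedure is added, and the primary endpoint and its power are untouched. The drawbacks are that the measure becomes a composite, which the component report addresses, and that one early death will still move an arm mean by a day or more at this sample size, now in the right direction.

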9.3 Implications of the findings of the event-adjudicating committee

The events will be adjudicated only after the completion of the study, and therefore the findings by the committee will have no implications on the conduct of the study.

10) DISCONTINUATION OF TREATMENT AND WITHDRAWAL

10.1 Reasons for Discontinuation of Treatment or Withdrawal from the Study

Patients may withdraw from the study at any time. The investigators may temporarily suspend treatment at any time in patients experiencing an adverse event considered possibly, probably, or definitely related to the study drug. The study drug may then be restarted upon resolution of the adverse event unless the adverse event is considered likely to reoccur or the patient is unwilling to restart treatment. The investigators can withdraw any patient at any time from the study if medically necessary. It will be extremely important to obtain complete follow-up data on each patient, except on those who withdraw consent to release such information. It will be documented whether or not each patient completed the study. If for any reason the study treatment or observations were discontinued, the reasons will be recorded and the IRB will be informed.

Reasons for discontinuation of Anakinra (or placebo):

- 1) Systemic infection (sepsis)*;
- 2) Surgery*;
- 3) New diagnosis of cancer that requires local or systemic treatment;
- 4) Hypersensitivity reaction (rash, anaphylaxis, arthritis);
- 5) Severe injection site reactions*;
- 6) Need for immunosuppressant therapy;
- 7) Acute myocardial infarction or stroke*;
- 8) Severe neutropenia (<1,000/mm³) if there is a perception of increased infectious risk by the provider*.

* treatment may be restarted by investigators after the condition is resolved

10.2 Handling of Withdrawals

Patients who permanently stop study injection (whether due to adverse event, investigator decision, or patient decision) will be considered withdrawn from treatment. Patients that have withdrawn from treatment will still be offered to complete all the functional assessments to analyze data in an intention-to-treat strategy. Patients who have withdrawn from treatment will also be followed for the complete duration of 6 months follow-up to monitor for safety. Loss to follow-up can occur due to patients' withdrawal or unreported death. If patients are lost to follow up and their clinical condition cannot be established (alive vs dead, hospitalized vs not), they will be excluded from the initial analysis, and then reintroduced for sensitivity analysis considering all potential outcomes.

Patients will be considered withdrawn from study if they express a desire to stop active participation. However, the investigators will continue to record adverse events, hospitalizations, and survival in these patients from the electronic medical record in an observational manner unless these patients withdraw consent. Upon withdrawal of consent, no further information will be collected from those patients.

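### Section 10.2 excludes lost patients of unknown status from the initial event analysis, although the planned time-to-event methods could use their follow-up to last contact

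*Combined protocol and SAP*

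**What the plan says.** The trigger in section 10.2 is narrow: "If patients are lost to follow up and their clinical condition cannot be established (alive vs dead, hospitalized vs not"). For those patients the rule is that "they will be excluded from the initial analysis, and then reintroduced for sensitivity analysis considering all potential outcomes". The same section says that "Loss to follow-up can occur due to patients' withdrawal or unreported death". It also limits how many patients should fall under the rule. Those who stop treatment are followed for the full 6 months. For those who leave the study, "the investigators will continue to record adverse events, hospitalizations, and survival in these patients from the electronic medical record", unless they withdraw consent.

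The event analysis is described elsewhere. Section 9.2 states: "The analysis will consider time to first event and time to each event". It adds event rates and hospital-free days at 1, 3 and 6 months. Section 11.3.1 plans "Kaplan-Meier curves with Log-rank testing for event rates" and defines intention-to-treat as analysis by randomized group of all patients who have outcome data. No section mentions censoring.

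On purpose, section 11.1 says the trial is not powered for 6-month admission rates, but "we believe this study will provide an estimate of the potential effect".

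**The concern.** A patient followed event-free to month 4 and then lost carries four months of information. Kaplan-Meier and log-rank are built to use it, and section 10.2 removes it. A patient lost in month 5 has fully known 1-month and 3-month outcomes, yet the rule does not distinguish by time point. It also does not say whether a patient readmitted in week 3 and then lost is kept or dropped. Read literally, an observed readmission can be deleted.

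The set analysed first therefore depends on what happened after randomization. Section 11.3.2 recognises this problem for peak VO2, where it rejects exclusion of patients with missing data because of survivorship bias. Section 10.2 accepts exclusion for events. At stake is the exploratory estimate of the readmission effect, which sections 4 and 11.1 name as something the trial should deliver.

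**Working it through.** **The plan's own figures.** The documents give no sample size, power or precision for the event analysis. The only loss figure is the 20% for loss or withdrawal in section 11.2, which belongs to the peak VO2 power. That calculation reproduces (normal approximation, two-sided 0.05, difference 1.6, SD 2.0):
- 68 vs 34: 1.6 / (2.0 × √(1/68 + 1/34)) − 1.96 = 1.85, power 0.968 (stated 0.97).
- 54 vs 27 after 20% loss: 1.6 / (2.0 × √(1/54 + 1/27)) − 1.96 = 1.43, power 0.924 (stated above 90%).

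**Inputs for the event check.** 6-month readmission of 5% (12-week anakinra) and 30% (placebo) from the pilot in section 4; 68 and 34 patients; 20% loss, varied from 5% to 30%. Exponential event and loss times, and loss independent of outcome, are assumptions of this check.

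**Formulas.** Let p be the 6-month event risk, q the 6-month loss risk, a = −ln(1 − p) and b = −ln(1 − q).
- Event seen before loss: E = a/(a + b) × [1 − (1 − p)(1 − q)]
- Lost event-free: L = b/(a + b) × [1 − (1 − p)(1 − q)]
- Complete and event-free: C = (1 − p)(1 − q)

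**Reading A: events before loss are kept and event-free lost patients are dropped.** Nobody is then censored before 6 months, so the Kaplan-Meier estimate equals the crude rate E/(E + C). At 20% loss:
- Anakinra: E = 0.0513/0.2744 × 0.24 = 0.0449; C = 0.76; rate 0.0449/0.8049 = 5.6%.
- Placebo: E = 0.3567/0.5798 × 0.44 = 0.2707; C = 0.56; rate 0.2707/0.8307 = 32.6%.

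| Loss, both arms | Anakinra | Placebo | Difference (true −25) |
|---|---|---|---|
| 5% | 5.1% | 30.6% | −25.5 |
| 10% | 5.3% | 31.2% | −25.9 |
| 20% | 5.6% | 32.6% | −27.0 |
| 30% | 6.0% | 34.2% | −28.3 |

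With no true effect (30% in both arms), loss of 10% vs 20% gives 31.2% vs 32.6%, a spurious 1.4 points. Loss of 5% vs 30% gives 30.6% vs 34.2%, about 3.7 points. The documents give no basis for expecting unequal loss; these cases only show the mechanism.

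**Reading B: every lost patient is dropped, including those with an earlier event.** Under independent loss the rates stay at 5.0% and 30.0%, so there is no bias.

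**Precision at 20% loss** (20,000 simulations per arm), standard errors in percentage points:

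| Handling | Anakinra | Placebo |
|---|---|---|
| Censor at last contact | 2.8 | 8.4 |
| Reading A | 3.1 | 8.9 |
| Reading B | 3.0 | 8.9 |

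**Information discarded at 20% loss.** L = 0.195 and 0.169, so about 68 × 0.195 = 13 and 34 × 0.169 = 6 patients are lost event-free, after 2.9 and 2.7 months on average. That is 10% to 11% of the event-free person-time.

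**Range of the all-outcomes analysis at 20% loss.** Event rates can run from E to E + L: 4.5% to 24.0% for anakinra and 27.1% to 44.0% for placebo. The difference runs from 4.5 − 44.0 = −39.5 to 24.0 − 27.1 = −3.1 points.

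**The case against.** The case against is substantial and most of it stands.

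- **Scope.** A reader might infer that everyone lost to follow-up is dropped for good. The text does not support that. Only patients of unestablished status are excluded, passive record follow-up continues unless consent is withdrawn, and the excluded patients return in a sensitivity analysis. The number affected should be below 20%, which is a conservative allowance for peak VO2 and not a forecast of unknown vital status.
- **Bias.** A reader might infer that exclusion always overstates event rates. That holds under Reading A with independent loss, not under Reading B. If loss reflects unreported death, which section 10.2 itself names, exclusion could understate mortality.
- **Censoring.** It is unbiased only if loss is independent of outcome, so it would not cure that last case either.
- **Intention-to-treat.** A reader might infer a flat contradiction of the principle. Section 11.3.1 limits it to patients with outcome data, so excluding patients of unknown outcome is arguably within its terms. Partial follow-up leaves the point debatable.
- **Stakes.** A reader might infer that the readmission estimate will size a phase III trial. Section 11.1 says only that a readmission signal would strengthen the rationale. The outcome is exploratory and unpowered.

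What this does not answer is why known follow-up should be discarded when the planned method can use it. The all-outcomes analysis does not fill the gap: at 20% loss its range of about 36 points is too wide to replace a main estimate.

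**Conclusion.** The point holds in a limited form. Section 10.2 does not fit the methods in sections 9.2 and 11.3.1, leaves open what happens to events seen before loss, and can bias the exploratory readmission estimate.

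The effect is small beside sampling error. At the upper-end assumption of 20% loss, Reading A shifts the difference by 2 points, against a standard error under censoring of about √(2.8² + 8.4²) = 8.9 points. The risk ratio hardly moves (0.171 against 0.167). At 5% to 10% loss the shift is under 1 point. Under Reading B with random loss there is only some loss of precision. These sizes rest on the pilot rates, exponential times and loss independent of outcome; the documents do not settle how far loss would be informative. The primary peak VO2 endpoint and its power are unaffected.

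**What to change.** State in sections 10.2 and 11.3 that:
- all randomized patients enter the event analyses from randomization;
- events documented before loss count;
- patients lost to follow-up are censored at the last date on which both vital and hospitalization status are documented;
- the 1-, 3- and 6-month event rates are the Kaplan-Meier estimates at those times.

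Keep the all-outcomes analysis as the sensitivity analysis, because censoring does not deal with informative loss such as unreported death.

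The cost is a short text change and a little data handling to establish the date of last known status. The documents do not say that this date is collected, so add it to the case report form if it is not already there. No visits, patients or changes to the primary analysis are needed.
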